9.4.2 Primary Endpoint

The primary endpoint is the proportion of participants who progress by at least one level higher on the modified WHO ordinal scale by Day 14.

9.4.3 Secondary Endpoint(s)

The key secondary endpoints are:

1. Change from baseline on the modified WHO ordinal scale at each visit up to Day 28
2. Change in room air SpO₂ from baseline over time
3. Change in NEWS 2 symptom score from baseline over time
4. Time to improvement of at least one level lower on the modified WHO ordinal scale
5. Time to progression of at least one level higher on the modified WHO ordinal scale

Additional secondary endpoints are:

1. Time to hospital discharge
2. Incidence of mortality by Day 28

9.4.4 Tertiary/Exploratory Endpoint(s)

CCI

- CCI

9.4.5 Other Safety Analyses

All safety analyses will be performed on the Safety Population.

1. Safety and tolerability assessed by clinical safety laboratory measurements, physical examinations, vital signs, concomitant medications; cumulative incidence of AEs, SAEs and severe AEs
2. Incidence of participants unable to tolerate nebulization due to:
 - Reduction in SpO₂ to < 90%, unless well clinically tolerated according to Investigator's opinion
 - Other clinical signs of intolerance according to Investigator's opinion
3. Incidence of clinical bronchial hyper-responsiveness related to nebulization

9.4.5.1 Adverse Events

Adverse Events will be coded using the MedDRA coding dictionary.

The number and percentage of participants with any AE, any related AE, any SAE, any related SAE, any severe AE, and related severe AE as well as the total number of events for each category will be summarized. The number of deaths due to an AE, hospitalization due to an AE, and study discontinuation due to an AE will be summarized.

The number and percentage of participants with an AE, as well as the total number of AEs, will be summarized by SOC and preferred term. This tabulation will be repeated for related AEs, SAEs, related SAEs, severe AEs, and related severe AEs.

All AEs will be provided in patient listings. Patient listings of AEs causing discontinuation of study medication, AEs leading to death, SAEs, related AEs, and severe AEs will be produced.

9.4.5.2 Clinical Laboratory Evaluation

Baseline is defined as the last non-missing value obtained at the screening visit and prior to the first exposure to study drug. Actual values and changes from Baseline clinical laboratory tests will be summarized by study day. If more than one laboratory result is reported per study visit per parameter, the last non-missing result will be selected for change from Baseline analysis.

Laboratory test results will be classified according to the reference ranges and clinical significance as determined by the Investigator. The number of participants with a non-missing result, the number and percentage of participants with a clinically significant result less than the lower limit of normal, non-clinically significant result more than the ULN, and clinically significant result more than the ULN will be summarized by study visit. If more than one laboratory result is reported per study day per parameter, the result yielding the most severe classification will be selected for analysis.

Categorical laboratory test results (urinalysis excluding pH) will be summarized by study visit. If more than one laboratory result is reported per study day per parameters, the result yielding the most severe classification will be selected for analysis.

Participants who had urine pregnancy test at screening and the results will be listed.

Participants with clinically significant abnormal laboratory test results will be listed. This listing will include all results of the laboratory parameter that was abnormal and determined to be clinically significant by the Investigator for a participant across study visit.

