5.3 Exclusion Criteria

Participants are excluded from the study if any of the following criteria apply:

Medical Conditions

1. Rapidly deteriorating or likely to require escalation to high flow oxygen, invasive or non-invasive ventilatory support within 24 hours according to Investigator's opinion.
2. Unable to safely receive a nebulized treatment for approximately 8 minutes according to Investigator's opinion.
3. Unable to receive or considered ineligible for invasive or non-invasive ventilatory support.
4. History of methemoglobinemia.
5. Uncontrolled asthma or history of severe bronchospasm.
6. Severe (requiring baseline oxygen therapy > 12 h/day prehospitalization) chronic respiratory disease (e.g., known COPD, pulmonary arterial hypertension, idiopathic pulmonary fibrosis, interstitial lung disease).
7. Suspected or confirmed untreated, active tuberculosis.
8. Severely immune-compromised participants in Investigator's opinion.
9. Recent (within 3 months) active coronary artery disease or decompensated heart failure (New York Heart Association class 3-4).
10. Presence of tracheostomy.

Prior/Concomitant Therapy

11. Chronic (≥ 4 weeks) use of corticosteroids >10 mg/day of prednisone or equivalent within 4 weeks of randomization.

Prior/Concurrent Clinical Study Experience

12. Participation in other clinical investigations utilizing investigational treatment or within 30 days / 5 half-lives whichever is longer.

Diagnostic Assessments

13. Clinically significant abnormalities in clinical chemistry or hematology at screening, defined as:
 - Methemoglobin level >2%
 - Platelet count <50,000 mm³
 - Alanine aminotransferase or aspartate aminotransferase >5 × upper limit of normal (ULN).
 - Estimated glomerular filtration rate <30 mL/min/1.73 m² (modification of diet in renal disease formula) or requiring hemofiltration or dialysis.

Other Exclusions

14. Anticipated transfer to another hospital which is not a study site during the treatment period.
15. Allergy to any of the components of the study intervention.

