7.1 Permanent Discontinuation of Study Intervention

It may be necessary for a participant to permanently discontinue (definitive discontinuation) study intervention. If study intervention is definitively discontinued, the participant will remain in the study to be evaluated for the Day 14 and Day 28 safety follow-ups. See the SoA (Table 1-1) for data to be collected at the time of discontinuation of study intervention and follow-up and for any further evaluations that need to be completed.

Study intervention will be permanently discontinued prior to 10 days if the participant:

- Improves to level 1 or 2 of the modified WHO ordinal scale;
- Progresses to a level > 4 of the modified WHO ordinal scale.

Additionally, study intervention should be permanently discontinued in the following circumstances:

1. Discontinuation of study intervention for abnormal liver tests should be considered if the Investigator believes that it is in best interest of the participant. The development of alanine aminotransferase (ALT) $\geq 3 \times$ ULN and bilirubin $\geq 2 \times$ ULN or ALT $\geq 3 \times$ ULN and international normalized ratio (INR) > 1.5 , if INR is measured, which may indicate severe liver injury (according to Hy's Law), must be reported as an SAE and the study intervention discontinued.
2. If, as part of normal clinical follow-up, a clinically significant change in ECG is identified, the Investigators should exercise their clinical judgement to decide whether continuing study intervention administration is in the best interest of safety of the participant.
3. AE/SAE if the Investigator believes that it is in best interest of the participant, including the following:
 - Development of significant bronchospasm * or worsening of cough that is not tolerated by the participant and leads to immediate discontinuation of the nebulization.
 - Progressive COVID-19 requiring initiation of invasive ventilation or high flow oxygen.
 - Development of mHb level above 3%.

- Inability to safely continue receiving study intervention due to compromised respiratory status while off supplemental oxygen and receiving nebulized therapy (manifest by drop in SpO₂, increased respiratory rate or clinical other findings).

Refer to the SoA (Table 1-1) for data to be collected at the time of study intervention discontinuation and follow-up and for any further evaluations that need to be completed.

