8.2.4 Clinical Safety Laboratory Assessments

Refer to Appendix 3 for the list of clinical laboratory tests to be performed and to the SoA (Table 1-1) for the timing and frequency.

The Investigator must review the laboratory report, document this review, and record any clinically relevant changes occurring during the study in the AE section of the CRF. The laboratory reports must be filed with the source documents. Clinically relevant abnormal laboratory findings are those which are not associated with the underlying disease, unless judged by the Investigator to be more severe than expected for the participant's condition.

All laboratory tests with values considered clinically abnormal during participation in the study or within 4 days after the last dose of study intervention should be repeated until the values return to normal or baseline or are no longer considered clinically significant by the Investigator or Medical Monitor.

- If such values do not return to normal/baseline within a period of time judged reasonable by the Investigator, the etiology should be identified, where possible, and the Sponsor notified.

- All protocol-required laboratory assessments, as defined in Appendix 3, must be conducted in accordance with the Laboratory Manual and the SoA (Table 1-1).
- If laboratory values from laboratory assessments not specified in the protocol and performed at the institution's local laboratory result in the need for a change in participant management or are considered clinically relevant by the Investigator (e.g., are considered to be an SAE or an AE), then the results must be recorded in the CRF.

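### The last-result rule for laboratory change from baseline can drop a methemoglobin (mHb) excursion when the repeat test falls in the same visit; a minor, cheap fix

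*Protocol*

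**What the plan says.** Section 9.4.5.2 of the current protocol holds two selection rules. For change from baseline, where a study visit has more than one result for a parameter, "the last non-missing result will be selected for change from Baseline analysis". For the table of abnormal results the rule is different: "If more than one laboratory result is reported per study day per parameter, the result yielding the most severe classification will be selected for analysis". The categories of that table are set as follows: "Laboratory test results will be classified according to the reference ranges and clinical significance as determined by the Investigator". The section also lists participants with clinically significant abnormal results: "This listing will include all results of the laboratory parameter that was abnormal and determined to be clinically significant by the Investigator".

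Section 8.2.4 says clinically abnormal values "should be repeated until the values return to normal or baseline or are no longer considered clinically significant". It does not say to which visit a repeat belongs. It also asks the Investigator to "record any clinically relevant changes occurring during the study in the AE section of the CRF".

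Two mHb limits matter here. Section 7.1 gives "Development of mHb level above 3" percent among the adverse event reasons for permanent discontinuation. Section 5.3, criterion 13, excludes "Methemoglobin level >2" percent at screening. Footnote 4 of the Schedule of Activities puts mHb at screening, at Days 1, 3, 7 and 10 or early withdrawal, and at Day 28 for those still in hospital.

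**The concern.** Methemoglobinemia is one of the risks named for RESP301 in Table 2-1. An abnormal mHb triggers further tests, and those tests continue until the value has settled. A rule that keeps the latest result within a visit will then tend to keep the settled value and discard the one that prompted the repeat. The error runs in one direction, towards no change, and mainly affects the arm in which excursions occur. The rule stands in the protocol itself, so an analysis plan that follows it inherits the problem and one that departs from it contradicts the protocol.

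At stake is how clearly one descriptive safety summary shows a treatment effect on mHb, and whether any planned output shows, by arm and without relying on judgment, how many participants passed the limit that the protocol acts on.

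**Working it through.** There is no stated figure to reproduce. The check sets the passages together and then sizes the effect on assumed values.

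**Step 1: when the rule bites.** Three things must coincide: a scheduled mHb is abnormal, a repeat is taken, and the repeat is assigned to the same study visit. Section 9.4.5.2 then selects the repeat. Section 8.2.4 leaves the third condition open. Section 9.4.5.2 adds to the uncertainty, because it presents changes by study day but selects one result per study visit. A repeat held as an unscheduled or later-day record would not replace the scheduled value.

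**Step 2: where else the excursion appears.**
- Abnormal-result table: kept, because the most severe classification is taken. The upper categories are above the upper limit of normal (ULN), split by the Investigator's view of clinical significance. Testing is local (Appendix 3), and the current sections fix no ULN for mHb. The rationale for the current amendment puts normal below 1%, while entry is allowed up to 2%. If the ULN is 1%, a stable 1.5% and a rise from 0.8% to 3.5% are both above it, and only the judgment of clinical significance separates them.
- Listing: kept, with all results for that parameter, if the Investigator judges a value clinically significant.
- Adverse event tables (Section 9.4.5.1): kept by preferred term if reported as an event, and in the discontinuation listing if that event stops treatment.
- Count above 3%: none of these outputs is defined by that limit.

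**Step 3: size, as an illustration.** The one input from the protocol is n = 200 on RESP301 (Section 9.2). Assumed inputs: baseline 0.8%; scheduled value at the peak, P = 3.5% or 5.0%; same-visit repeat 1.0%; a fraction f of 1%, 5% or 10% with such an excursion; no change in the others.

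Mean change with the last result = f × (1.0 − 0.8). Mean change with the scheduled (peak) result = f × (P − 0.8).

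| f | Participants | Last result | Peak, P = 3.5% | Peak, P = 5.0% |
|---|---|---|---|---|
| 1% | 2 | 0.01 × 0.2 = 0.002 | 0.01 × 2.7 = 0.027 | 0.01 × 4.2 = 0.042 |
| 5% | 10 | 0.05 × 0.2 = 0.010 | 0.05 × 2.7 = 0.135 | 0.05 × 4.2 = 0.210 |
| 10% | 20 | 0.10 × 0.2 = 0.020 | 0.10 × 2.7 = 0.270 | 0.10 × 4.2 = 0.420 |

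The understatement is f × (P − 1.0): 0.025 to 0.040 points at 1%, 0.125 to 0.200 at 5%, and 0.250 to 0.400 at 10%. If only a share s of the repeats is booked to the same visit, these figures are multiplied by s and vanish at s = 0.

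With an assumed ULN of 1%, the existing most-severe rule counts all 2, 10 or 20 participants as above ULN. It does not separate those above 3% from those between 1% and 3%.

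**The case against.** The strongest reply is that very little is lost. The paragraph after the last-result rule selects the worst classification, the listing shows peak and repeats together, and an mHb that stops treatment should reach the adverse event tables. Threshold counts, maxima and shift tables are commonly left to the analysis plan, which is not at hand. All of this stands. It limits the point to one stated rule in one descriptive summary; the absence of a count above 3% is not a finding in its own right.

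Four stronger conclusions that a reader might draw are not supported:
- That the selected value must be the recovered one. Repeats are tied to no visit, and they may stop at baseline or when no longer clinically significant, as well as at normal.
- That passing 3% is never summarized. It enters the adverse event tables if reported as an event. The accurate statement is that no output in the protocol is defined by that limit.
- That the abnormal-result table cannot tell a rise from a permitted entry value. It splits results by clinical significance, and criterion 13 treats mHb as clinically significant at screening only above 2%. The separation is possible but rests on judgment made with the arm known.
- That the size is established. The peak, the repeat and the frequency are all assumed. The only mHb figure the protocol gives for inhaled nitrite is below 3%.

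A further fair objection is that a maximum is not neutral. Repeats follow abnormal values, so the arm tested more often has more chances of a high reading. That is answered by showing the testing frequency, and it is a reason not to make the maximum the by-visit value.

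**Conclusion.** The point holds as a minor one. The stated last-result rule, read with the repeat-testing rule, biases the mHb change-from-baseline summary towards no change whenever a repeat is assigned to the same visit. The excursion remains visible in other outputs, but those depend on the local ULN or on Investigator judgment in an open-label trial. The size is unknown. The illustration gives an understatement of 0.025 to 0.400 points on the arm mean at a visit, for 1% to 10% of participants affected, and it rests on the assumed values and on every repeat being booked to the scheduled visit. The primary efficacy analysis is untouched.

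**What to change.** In Section 9.4.5.2, and in the analysis plan to match:
- State that repeat or unscheduled mHb results do not replace the scheduled result in the by-visit change-from-baseline summary.
- Summarize by arm each participant's maximum post-baseline mHb, and the number and percentage above the protocol's existing 3% limit. The maximum covers excursions caught only by an unscheduled test.
- Show the number of mHb measurements per arm beside it, so that a difference in testing frequency can be seen.

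The cost is one sentence and one more table, from values already collected. The downside is some inflation of the maximum where testing is more frequent, which the measurement counts make visible. Nothing here implies a change to the 3% limit, the entry limit, repeat testing or any other clinical management.

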9.4.5.3 Vital Signs

Baseline is defined as the last non-missing value obtained in screening and prior to the first exposure to study drug. Actual values and changes from Baseline in vital signs will be summarized by study day and study time point. All vital sign data will be presented in patient listings.

Vital sign values will be classified according to the clinical significance as determined by the Investigator. The number of participants with a non-missing result, the number and percentage of participants with a non-clinically significant result, and clinically significant result will be summarized by study visit and study time point. If more than one vital sign result is reported per study day and study time point per parameter, the result yielding the most severe classification will be selected for analysis.

Participants with clinically significant vital sign values will be listed. This listing will include all results of the vital sign parameter that was determined by the Investigator to be clinically significant for a participant across study time points.

9.4.5.4 Physical Examination

Abnormal physical examination findings will be listed.

9.4.6 Other Analyses

Other analyses may be added to the SAP as applicable.

9.5 Interim Analyses

Two interim analyses will be performed.

1. The first analysis will be conducted when about 60 participants (40 participants in the RESP301+SOC arm and 20 participants in the SOC arm) have completed the Day 10 assessment. The purpose of this analysis is to evaluate efficacy of RESP301 with the application of a futility criterion based on the results on SpO₂ change from baseline on Day 10. The following futility criterion will be used for this first interim analysis:

If the difference in the percentage of participants with at least a 2% improvement in SpO₂ between both treatment arms is less than 5%, benefit of RESP301 treatment is not expected. For a final decision to stop the study for futility the results on other endpoints will be considered as well.

As no other modification of the study at the time of the first interim analysis is considered, no adjustment of the alpha level is required.

2. The second interim analysis will be conducted after 150 participants (100 participants in the RESP301+SOC arm and 50 participants in the SOC arm) have completed the Day 14 assessment. The purpose of this analysis is the assessment of futility or a sample size re-estimation in case the actual results differ from the original assumptions for the power calculations of the study, related to the percentage of participants meeting the primary endpoint in the control arm and/or the relative treatment benefit achieved in the RESP301+SOC arm compared to the SOC arm.

To account for the multiple testing due to the second interim analysis an adjustment for the type I error alpha will be applied using the Haybittle-Peto approach which would spend one sided alpha=0.0005 at the second interim analysis and leave one-sided nominal alpha of 0.0249 for the final analysis. The futility criterion for the second interim analysis will be based on the conditional power (CP) for the final results based on the assumption that the remainder of the study will follow the same trend as observed in the interim analysis. If CP at the time of the second interim analysis is less than 20% consideration will be given to stop the study for futility. At the same time sample size re-estimation will be performed to achieve 80% power at the end of the study. The methodology for the adjustment and the procedure to maintain the type I error level will be described in greater detail in the SAP.

Detailed information, including the boundaries futility and characteristics for the sample size re-estimation at the time of the interim analyses will be provided in the SAP and Data Monitoring Committee (DMC) Charter. Further details are also provided in Appendix 5.

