9.2 Sample Size Determination

A total of 300 hospitalized participants with confirmed COVID-19 will be randomized 2:1 to receive RESP301+SOC (200 participants) or SOC alone (100 participants).

The comparison between the treatment arms for the primary endpoint will have approximately 80% power and alpha level 0.025 (one-sided) to demonstrate significant reductions (15% versus 30%) of the primary endpoint between RESP001+SOC and the Control arm (SOC), a 50% relative reduction for the proportion of participants who progress by at least one level on the WHO ordinal scale (see definition of the primary endpoint).

Two interim analyses are planned (see Section 9.5 for details):

1. The first IDMC interim analysis will take place after the first 60 participants have completed Day 10 of the study to evaluate whether the study can be stopped for futility based on change from baseline in room air SpO₂. For a final decision to stop the study for futility the results on other endpoints will be considered as well.
2. The second interim analysis will take place after 150 participants have completed Day 14 post-randomization based on event rate for the primary endpoint. The purpose of the second interim analysis will be futility as well as a potential sample size re-estimation in case the actual results differ from the original assumptions.

In addition to the review of efficacy data, safety will be assessed at each of the interim analysis by the IDMC. Further details are provided in Appendix 5.

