3. Non-binding DMC guidance for stopping the study for futility at the first interim analysis is stated as:

If the difference in the percentage of participants with at least a 2% improvement in SpO₂ between both treatment arms is less than 5%, a benefit of RESP301 treatment is not expected. For a final decision to stop the study for futility the results on other endpoints will be considered as well.

As the main futility stopping criterion is based on improvement in SpO₂ (and not on the primary efficacy endpoint), this first interim analysis will be “ignored” in these statistical considerations for an adaptive group-sequential design. We may revisit the first interim analysis at a later point in time when more information is available.

4. Non-binding DMC guidance for stopping the study for futility at the second interim analysis stated as:

The futility criterion for the second interim analysis will be based on the conditional power (CP) for the final results based on the assumption that the remainder of the study will follow the same trend as observed in the interim analysis. If CP at the time of the second interim analysis is less than 20% consideration will be given to stop the study for futility.

5. Current DMC guidance for stopping the study for superior efficacy at the second interim analysis is stated as:

To account for the multiple testing due to the second interim analysis an adjustment for the type-I-error probability will be applied using the Haybittle-Peto approach with one sided alpha=0.0005 at the second interim analysis and leave one-sided nominal alpha of 0.0249 for the final analysis.

6. For initial sample size calculation, the following additional assumptions / features from the protocol have been used

- progression probability up to Day 14 for Standard of Care (SOC): 30%

- progression probability up to Day 14 for RESP301+SOC: 15%
- desired power assuming the alternative hypothesis stated above: 80%
- 2:1 randomization

7. Method for adaptation of the sample size based on the second interim analysis data is stated as

A sample size re-estimation will be performed to achieve 80% conditional power at the end of the study. The methodology for the adjustment and the procedure to maintain the type-I-error level will be described in greater detail in an appendix to the protocol. The maximum increase of the sample size will be limited to a total number of 600 randomized subjects.

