10.5.3 Adaptive Sample Size Re-Estimation

Another objective of the 2nd interim analysis is to re-estimate the sample size based on the unblinded interim results.

Proposed procedure at 2nd interim analysis (planned to include approximately 150 subjects)

- unblinded analysis of the primary efficacy endpoint (“Proportion of participants who progress by at least one level higher on the modified WHO ordinal scale by Day 14” as a binary endpoint)
- calculation of conditional power (CP) given the interim results and calculated by assuming the interim estimates to be the true distribution parameters for the remaining part of the study
 - if $CP < 4\%$: recommend early stop for futility
 - if one-sided p-value < 0.0005 : recommend early stop for superior efficacy
 - if $50\% < CP < 80\%$ and one-sided p-value ≥ 0.0005 :
 - continue the study with an increased total sample size N^* , so that CP with a total of N^* subjects is increased to 80%, same value as the (unconditional) desired power in the study design
 - N^* , however, is limited to 600 (which is twice the original sample size 300)
 - if $4\% \leq CP \leq 50\%$: continue the study without a change in sample size (otherwise, the sample size would need to be increased too much or the maximum sample size of 600 would not be sufficient to come close to a CP of 80%).

The table on the next page illustrated the proposed procedure for a number of possible results observed at the 2nd interim analysis.

Table with examples for the adaptive sample size procedure described above using the Cui/Hung/Wang (CHW) approach using a weighted (fixed weights determined by the stage-wise sample sizes planned at the design-stage) test for the final analysis:

2 nd IA results with n=150 subjects (50 for SOC, 100 for RESP301+SOC)		CP under observed trend for planned 300	Total sample size required for CP 80% under observed trend	CP under observed trend if total sample size capped by 600
15 (30%)	5 (5%)	$p < 0.0005 \rightarrow$ early stop for superior efficacy		
15 (30%)	10 (10%)	99%	Not applicable	Not applicable
15 (30%)	15 (15%)	90%	Not applicable	Not applicable
15 (30%)	18 (18%)	66%	393	Not applicable
15 (30%)	19 (19%)	55%	483	Not applicable
15 (30%)	21 (21%)	34%	[798]	[67%]
15 (30%)	26 (26%)	3.99%	Early stop for futility	
12 (24%)	10 (10%)	92%	Not applicable	Not applicable
12 (24%)	12 (12%)	77%	321	Not applicable
12 (24%)	14 (14%)	54%	498	Not applicable
12 (24%)	15 (15%)	42%	[646]	[77%]
12 (24%)	18 (18%)	14%	[1800]	[31%]

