10.5.4 Overall Adaptive Design Performance

Finally, the Cui/Hung/Wang (CHW) approach is compared to the Chen/DeMets/Lan (CDL) approach without pre-defined fixed weights for the final analysis (which is valid as sample size may only be increased if CP (obtained under observed trend) at the second interim analysis exceeds 50%).

All the results below are for the group-sequential design with adaptive sample size re-estimation procedure as described in previous sections and based on 10.000 simulated trials each.

Scenario 1: true progression probabilities are 30% (SOC) and 15% (RESP301+SOC)

Scenario 2: true progression probabilities are 24% (SOC) and 14% (RESP301+SOC)

Scenario 3: true progression probabilities are 30% (SOC) and 10% (RESP301+SOC)

Scenario 4: true progression probabilities are 24% (SOC) and 20% (RESP301+SOC)

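### Section 9.5 promises 80% power after sample size re-estimation; the Appendix 5 rule targets 80% conditional power in one zone only and does not restore study power when rates differ from plan

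*Protocol*

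**What the plan says.** Section 9.2 of the Protocol (current version, WHO levels 3 and 4) fixes the design: "A total of 300 hospitalized participants with confirmed COVID-19 will be randomized 2:1", with "approximately 80% power and alpha level 0.025 (one-sided) to demonstrate significant reductions (15% versus 30" per cent.

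Section 9.5 gives the second interim, at 150 participants, two purposes: futility, and re-estimation of the sample size if the control-arm event rate or the relative benefit is not as assumed. Having described a futility criterion based on conditional power, it continues: "At the same time sample size re-estimation will be performed to achieve 80% power at the end of the study". It leaves the method to the SAP and DMC Charter and adds: "Further details are also provided in Appendix 5".

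Appendix 5 describes the same step in other terms. Item 7 of Section 10.5.1 reads: "A sample size re-estimation will be performed to achieve 80% conditional power at the end of the study", with a maximum of 600. Section 10.5.3 gives the working rule: an increase only for CP above 50% and below 80%, to an N at which CP for those "subjects is increased to 80%, same value as the (unconditional) desired power in the study design". For CP from 4% to 50% the trial continues at 300, and below 4% a futility stop is recommended. Section 10.5.4 lists four simulation scenarios, among them "Scenario 2: true progression probabilities are 24% (SOC) and 14% (RESP301+SOC").

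**The concern.** The sentence in 9.5 stands in a paragraph about rates that differ from plan, and that paragraph has already introduced conditional power as a separate term. A reader will therefore take the unqualified word power to mean the power of the study, and will take re-estimation as a safeguard of that power against a lower control rate or a smaller benefit.

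The rule in 10.5.3 is not such a safeguard. It acts on one band of interim results, and its target is computed as if the interim estimate were the truth. The two sections even prescribe different actions. For CP between 20% and 50%, which is above 9.5's own futility limit, 9.5 implies an increase and 10.5.3 rules one out.

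The safeguard matters because level 3 patients, and progression from level 3 to 4, have been added to the study while 30% v 15% and N=300 were kept. The control rate could now lie on either side of 30%. An IDMC, sponsor or regulator relying on 9.5 alone would overestimate how well the design copes with that.

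**Working it through.** **Inputs.** Planned rates 30% v 15%, N=300, 2:1 (9.2). Second interim at 50 v 100 patients, and alpha: "spend one sided alpha=0.0005 at the second interim analysis and leave one-sided nominal alpha of 0.0249 for the final analysis" (9.5). CP zones, cap of 600 and the fixed-weight Cui/Hung/Wang test (10.5.3). Alternative rates: 24% v 14% is Scenario 2 of 10.5.4. The pairs 24% v 12% and 20% v 10% are assumptions that keep the planned 50% relative reduction at lower control rates.

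**Formulas.** With equal planned stages, the final statistic is √0.5·z1 + √0.5·z2, with critical value 1.9617 (one-sided 0.0249). Stage 2 must therefore exceed t = 1.9617/√0.5 − z1 = 2.7742 − z1. Under the observed trend at N=300, CP = Φ(z1 − t). The total N for 80% CP is N* = 150 + 150·((t + 0.8416)/z1)².

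**Step 1: reproduce the plan's own figures.**
- Sample size at 30% v 15% with continuity correction: 291 at alpha 0.025 and 294 at 0.0249, against 300 stated.
- Power at 30% v 15%, N=300, CP<4% stop, no re-estimation, unpooled variance: 81.1%, against about 80% stated.
- 15/50 v 18/100, unpooled: z1 = 0.12/√(0.0042 + 0.001476) = 1.593; t = 1.181; CP = Φ(0.411) = 66%; N* = 150 + 150·(2.023/1.593)² = 392. Stated: 66% and 393.
- 12/50 v 15/100, unpooled: z1 = 0.09/√(0.003648 + 0.001275) = 1.283; t = 1.492; CP = Φ(−0.209) = 42%; N* = 646. Stated: 42% and [646]. Under 10.5.3 this trial stays at 300, although its CP is far below 80%.

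So the rule modelled here is the rule written, and within its zone it gives the conditional power it is set to give.

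**Step 2: unconditional power of the full rule.** At least 300,000 simulated trials per cell: efficacy stop at p<0.0005, futility stop at CP<4%, increase for 50%<CP<80%, cap 600, fixed-weight final test at 0.0249. Each cell is unpooled / pooled variance.

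| True rates | Power | N raised in |
|---|---|---|
| 30% v 15% (plan) | 83% / 85% | 16% / 14% |
| 24% v 14% | 54% / 57% | 18% / 17% |
| 24% v 12% | 71% / 75% | 18% / 17% |
| 20% v 10% | 61% / 66% | 18% / 17% |

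At 24% v 14%, power without re-estimation is 50.8% / 55.0%; with it, 53.6% / 57.5%. The gain is 2.8 / 2.5 points. The unweighted Chen/DeMets/Lan test gives 53.7% / 57.0%, so the choice of final test is immaterial. With the 20% futility limit of 9.5 in place of 4%, power is about 50% / 53%.

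**Step 3: why the gain is small.** At 24% v 14% the trials divide as follows (unpooled / pooled):
- futility stop: 17% / 17%
- CP of 4–50%, N stays at 300: 30% / 27%
- N raised: 18% / 17%
- CP of at least 80%, or efficacy stop: 35% / 39%

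Even where N is raised, only about 74–76% of trials succeed at these rates, because 80% is conditional on the observed trend and not on the true one.

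**The case against.** The strongest case against is that the meaning is recoverable. Item 7 of 10.5.1 gives nearly the same sentence with the word conditional in it, and 9.5 refers to Appendix 5. Section 10.5.3 separates conditional from unconditional power, states the zone and cap, and explains why N is not raised for CP of 4–50%. All of this stands. It limits the correction to 9.5 and a small addition to item 7, which omits the zone. It does not make the sentence in 9.5 true: even read as conditional power, it fails for trials with CP of 4–50%.

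Three stronger readings are tempting, and the documents do not support them.
- *The stated power is wrong.* No section states 80% power at 24% v 14%. The only overall power figure is for 30% v 15% with N=300, and it reproduces.
- *The rule, not the cap, causes the shortfall.* A fixed design needs about 528 patients for 80% power at 24% v 14%, below 600, which suggests this. But that figure assumes the true effect is known in advance. If the zone is widened to CP of 4–80% under the same cap, power at these rates is still only 66–68%.
- *Operating characteristics are missing.* Section 10.5.4 announces simulation results for its four scenarios. They are not in the text available here and may already show these figures.

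It also cannot be said that the control rate will fall. The wider endpoint counts an extra kind of progression, so the direction is unknown.

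**Conclusion.** The concern holds as a mismatch between sections, not as an error in the power calculation. Section 9.5 asserts, for rates that differ from plan, a property that the written rule does not have and that Appendix 5 does not claim. Unconditional power under the rule is about 54–57% at 24% v 14%, 71–75% at 24% v 12% and 61–66% at 20% v 10%, and re-estimation contributes 2 to 3 of those points.

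These figures assume that the 10.5.3 rule is followed exactly with the 4% futility stop, an interim at exactly 50 v 100, an unstratified two-proportion test in place of the stratified Cochran–Mantel–Haenszel test, and no missing outcomes. The ranges span the two variance forms. The SAP is not at hand and may describe the method further, but the sentence in the Protocol would still need correcting.

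**What to change.** In Section 9.5, replace the sentence with wording such as: *If interim CP is between 50% and 80%, the total sample size is increased (maximum 600) to bring conditional power under the observed trend to 80%; otherwise it is unchanged. This does not guarantee 80% unconditional power if the true rates differ from 30% v 15%.* Cross-refer to 10.5.3.

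In item 7 of 10.5.1, add the 50–80% CP zone. Section 10.5.3 needs no change on this point.

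Beside the new sentence, give the unconditional power and the probability of an increase for 24% v 14%, 24% v 12% and 20% v 10%, or refer to the 10.5.4 results where these already give them. The 20% and 4% futility limits in 9.5 and Appendix 5 need reconciling in any case; the figures should be produced under whichever limit is kept.

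The cost is two wording changes and at most one short table, with no change to the design and no extra patients. The downside is that the protection described becomes visibly weaker.
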